### 7.1.2 Subject Exclusion Criteria

The subject must be excluded from participating in the trial if the subject:

- Has had prior radiation to affected area.
- Has one of the following sarcoma subtypes where neoadjuvant chemotherapy is established as practice at our institution: extra-skeletal Ewing's sarcoma, Embryonal Rhabdomyosarcoma, Alveolar Rhabdomyosarcoma

- a. **NOTE:** Pleomorphic rhabdomyosarcoma is allowed. Bone sarcomas including Osteosarcoma, Ewing's sarcoma and Chondrosarcoma are not allowed. Extra-skeletal Osteosarcoma is considered a soft tissue sarcoma and is allowed.
3. Has a diagnosis of immunodeficiency or has an active autoimmune disease that has required systemic treatment in the past 2 years except replacement therapy (e.g., thyroxine, insulin, or physiologic corticosteroid).
4. Is receiving systemic steroid therapy or any other form of immunosuppressive therapy within 7 days prior to the first dose of trial treatment.
5. Has a known history of active TB (Bacillus Tuberculosis).
6. Hypersensitivity ( $\geq$  Grade 3) to pembrolizumab and/or any of its excipients.
7. Has a history of a second malignancy, unless potentially curative treatment has been completed with no evidence of malignancy for 2 years.
  - a. **NOTE:** The time requirement does not apply to participants who underwent successful definitive resection of basal cell carcinoma of the skin, squamous cell carcinoma of the skin, superficial bladder cancer, in situ cervical cancer, or other in-situ cancers.
8. Has current or a history of any distant metastatic disease (including brain).
  - a. **NOTE:** An isolated or oligo-metastatic regional recurrence may be allowed if all other criteria are met, curative attempt is being pursued.
9. Has known history of (non-infectious) pneumonitis or interstitial lung disease that required steroids, or has current evidence of pneumonitis or interstitial lung disease.
10. Has an active infection requiring systemic therapy.
11. Has known psychiatric or substance abuse disorders that would interfere with adherence to the requirements of the trial.
12. Is pregnant (positive urine pregnancy test within 72 hours prior to enrollment) or breastfeeding, or expecting to conceive or father children within the projected duration of the trial, starting with the pre-screening or screening visit through 120 days after the last dose of trial treatment. If a urine pregnancy test is positive or cannot be confirmed negative, a serum pregnancy test will be required.
13. Has received prior therapy with an anti-PD-1, anti-PD-L1, anti-CTLA4 or anti-PD-L2 agent or with an agent directed to another stimulatory or co-inhibitory T-cell receptor (eg, CTLA-4, OX 40, CD137).

14. Has a known history of Human Immunodeficiency Virus (HIV) infection.
15. Has known history of Hepatitis B (e.g., HBsAg reactive) or Hepatitis C (e.g., HCV RNA [qualitative] is detected) infection.
16. Has received a live vaccine or live-attenuated vaccine within 30 days of planned start of study therapy. Administration of killed vaccines is allowed. *Note: Any licensed COVID-19 vaccine (including for Emergency Use) is allowed in the study as long as they are mRNA vaccines, adenoviral vaccines, or inactivated vaccines. These vaccines will be treated just as any other concomitant therapy. Investigational vaccines (i.e., those not licensed or approved for Emergency Use) are not allowed.*
17. Has received an investigational agent or has used an investigational device within 4 weeks prior to study intervention administration.
18. Has a history or current evidence of any condition, therapy, or laboratory abnormality or other circumstance that might confound the results of the study, interfere with the subject's participation for the full duration of the study, such that it is not in the best interest of the subject to participate, in the opinion of the treating investigator or has not adequately recovered from any major surgery or has ongoing surgical complications.
19. Has had an allogenic tissue/solid organ transplant.

## 7.2 Trial Treatments

The treatment to be used in this trial is outlined below in Table 2.

Table 2 - Trial Treatment

Drug	Dose/Potency	Dose Frequency	Route of Administration	Regimen/Treatment Period	Use
Pembrolizumab	200 mg	Q3W	IV infusion	Day 1 of each 3 week cycle x 3	Experimental
Radiation	≥45 Gy	Daily	N/A	5-6 weeks	Standard
Surgery	N/A	Once	N/A	N/A	Standard

### 7.2.1 Pembrolizumab

Pembrolizumab will be administered per institutional standard at the Fred Hutchinson Cancer Center as an outpatient therapy. Subjects will receive a maximum of three doses of pembrolizumab on study.

Pembrolizumab dose calculation, reconstitution, preparation of the infusion fluid, and administration will be completed per institutional standard, referencing the package insert.

### **7.2.1.1 Dose Selection/Modification**

#### **7.2.1.1.1 Dose Selection**

Subjects will receive a flat dose of 200 mg of pembrolizumab intravenously every 3 weeks, up to a maximum of three doses. Please refer to Table 2 - Trial Treatment for additional information.

#### **7.2.1.1.2 Dose Modification and Toxicity Management for Immune-Related AEs Associated with Pembrolizumab and Immuno-oncology (IO) combination partners**

AEs associated with pembrolizumab or IO/IO combination exposure, , may represent an immunologic etiology. These immune-related AEs (irAEs) may occur shortly after the first dose or several months after the last dose of pembrolizumab or combination treatment and may affect more than one body system simultaneously. Therefore, early recognition and initiation of treatment is critical to reduce complications. Based on existing clinical study data, most irAEs were reversible and could be managed with interruptions of pembrolizumab or combination treatment, administration of corticosteroids and/or other supportive care. For suspected irAEs, ensure adequate evaluation to confirm etiology or exclude other causes. Additional procedures or tests such as bronchoscopy, endoscopy, skin biopsy may be included as part of the evaluation. Based on the severity of irAEs, withhold or permanently discontinue pembrolizumab or combination treatment and administer corticosteroids. Dose modification and toxicity management guidelines for irAEs associated with pembrolizumab are provided in Table 3 and Table 6.

**Note:** The treatment guidelines are intended to be applied when the investigator determines the events to be related to pembrolizumab. If after the evaluation the event is determined not to be related to pembrolizumab, the investigator does not need to follow the treatment guidance.

**Table 3 - Dose modification and toxicity management guidelines for immune-related AEs associated with pembrolizumab and IO combination partners**

General instructions:				
Immune-related AEs	Toxicity grade or conditions (CTCAE v5.0)	Action taken to pembrolizumab	irAE management with corticosteroid and/or other therapies	Monitor and follow-up
Pneumonitis	Grade 2	Withhold	
 
Administer corticosteroids (initial dose of 1-2 mg/kg prednisone or equivalent) followed by taper
 
Add prophylactic antibiotics for opportunistic
 
	
 
Monitor participants for signs and symptoms of pneumonitis
 
Evaluate participants with suspected pneumonitis with radiographic imaging and initiate corticosteroid treatment
 

	Recurrent Grade 2, Grade 3 or 4	Permanently discontinue		
Diarrhea / Colitis	Grade 2 or 3	Withhold	
 
Administer corticosteroids (initial dose of 1-2 mg/kg prednisone or equivalent) followed by taper
 
	
 
Monitor participants for signs and symptoms of enterocolitis (ie, diarrhea, abdominal pain, blood or mucus in stool with or without fever) and of bowel perforation (ie, peritoneal signs and ileus).
 

	Grade 4	Permanently discontinue		
 
Participants with <math>\geq</math> Grade 2 diarrhea suspecting colitis should consider GI consultation and performing endoscopy to rule out colitis.
 
Participants with diarrhea/colitis should be advised to drink liberal quantities of clear fluids. If sufficient oral fluid intake is not feasible, fluid and electrolytes should be substituted via IV infusion.
 

AST / ALT elevation or Increased bilirubin	Grade 2 A	Withhold	
 
Administer corticosteroids (initial dose of 0.5- 1 mg/kg prednisone or equivalent) followed by taper
 
	
 
Monitor with liver function tests (consider weekly or more frequently until liver enzyme value returned to baseline or is stable)
 

	Grade 3 B or 4 C	Permanently discontinue	
 
Administer corticosteroids (initial dose of 1-2 mg/kg prednisone or equivalent) followed by taper
 
	
Type 1 diabetes mellitus (T1DM) or Hyperglycemia	Newly onset T1DM or Grade 3 or 4 hyperglycemia associated with evidence of $\beta$ -cell failure	Withhold D	
 
Initiate insulin replacement therapy for participants with T1DM
 
Administer anti-hyperglycemic in participants with hyperglycemia
 
	
 
Monitor participants for hyperglycemia or other signs and symptoms of diabetes.
 

Hypophysitis	Grade 2	Withhold	
 
Administer corticosteroids and initiate hormonal replacements as clinically indicated.
 
	
 
Monitor for signs and symptoms of hypophysitis (including hypopituitarism and adrenal insufficiency)
 

	Grade 3 or 4	Withhold or permanently discontinue D		
Hyperthyroidism	Grade 2	Continue	
 
Treat with nonselective beta-blockers (eg, propranolol) or thionamides as appropriate
 
	
 
Monitor for signs and symptoms of thyroid disorders.
 

	Grade 3 or 4	Withhold or permanently discontinue D		

Hypothyroidism	Grade 2-4	Continue	
 
Initiate thyroid replacement hormones (eg, levothyroxine or liothyroinine) per standard of care
 
	
 
Monitor for signs and symptoms of thyroid disorders.
 

Nephritis: grading according to increased creatinine or acute kidney injury	Grade 2	Withhold	
 
Administer corticosteroids (prednisone 1-2 mg/kg or equivalent) followed by taper.
 
	
 
Monitor changes of renal function
 

	Grade 3 or 4	Permanently discontinue		
Neurological Toxicities	Grade 2	Withhold	
 
Based on severity of AE administer corticosteroids
 
	
 
Ensure adequate evaluation to confirm etiology or exclude other causes
 

	Grade 3 or 4	Permanently discontinue		
Myocarditis	Asymptomatic cardiac enzyme elevation with clinical suspicion of myocarditis (previously CTCAE v4.0 Grade 1)	Withhold	
 
Based on severity of AE administer corticosteroids
 
	
 
Ensure adequate evaluation to confirm etiology and/or exclude other causes
 

	Grade 2, 3 or 4	Permanently discontinue		
Exfoliative Dermatologic Conditions	Suspected SJS, TEN, or DRESS	Withhold	
 
Based on severity of AE administer corticosteroids
 
	
 
Ensure adequate evaluation to confirm etiology or exclude other causes
 

	Confirmed SJS, TEN, or DRESS	Permanently discontinue		
All other immune-related AEs	Intolerable/ persistent Grade 2	Withhold	
 
Based on type and severity of AE administer corticosteroids
 
	
 
Ensure adequate evaluation to confirm etiology or exclude other causes
 

	Grade 3	Withhold or discontinue based on the type of event. E		

	Recurrent Grade 3 or Grade 4	Permanently discontinue		
AE(s)=adverse event(s); ALT= alanine aminotransferase; AST=aspartate aminotransferase; CTCAE=Common Terminology Criteria for Adverse Events; DRESS=Drug Rash with Eosinophilia and Systemic Symptom; GI=gastrointestinal; IO=immuno-oncology; ir=immune related; IV=intravenous; SJS=Stevens-Johnson Syndrome; T1DM=type 1 diabetes mellitus; TEN=Toxic Epidermal Necrolysis; ULN=upper limit of normal.				
Note: Non-irAE will be managed as appropriate, following clinical practice recommendations.				
A AST/ALT: >3.0 to 5.0 x ULN if baseline normal; >3.0 to 5.0 x baseline, if baseline abnormal; bilirubin: >1.5 to 3.0 x ULN if baseline normal; >1.5 to 3.0 x baseline if baseline abnormal				
B AST/ALT: >5.0 to 20.0 x ULN, if baseline normal; >5.0 to 20.0 x baseline, if baseline abnormal; bilirubin: >3.0 to 10.0 x ULN if baseline normal; >3.0 to 10.0 x baseline if baseline abnormal				
C AST/ALT: >20.0 x ULN, if baseline normal; >20.0 x baseline, if baseline abnormal; bilirubin: >10.0 x ULN if baseline normal; >10.0 x baseline if baseline abnormal				
D The decision to withhold or permanently discontinue pembrolizumab is at the discretion of the investigator or treating physician. If control achieved or $\leq$ Grade 2, pembrolizumab may be resumed.				
E Events that require discontinuation include, but are not limited to: encephalitis and other clinically important irAEs.				

#### **7.2.1.1.3 Dose Modification and Toxicity Management of Infusion-Reactions Related to Pembrolizumab**

Pembrolizumab or other drugs in combination may cause severe or life threatening infusion-reactions including severe hypersensitivity or anaphylaxis. Signs and symptoms usually develop during or shortly after drug infusion and generally resolve completely within 24 hours of completion of infusion. Dose modification and toxicity management guidelines on pembrolizumab associated infusion reaction are provided in Table 4.

Table 4 - Pembrolizumab Infusion-Reaction Dose modification and Treatment Guidelines

NCI CTCAE Grade	Treatment	Premedication at Subsequent Dosing
Grade 1 Mild reaction; infusion interruption not indicated; intervention not indicated	Increase monitoring of vital signs as medically indicated until the participant is deemed medically stable in the opinion of the investigator.	None
Grade 2 Requires therapy or infusion interruption but responds promptly to symptomatic treatment (e.g., antihistamines, NSAIDs, narcotics, IV fluids); prophylactic medications indicated for ≤24 hrs	
Stop Infusion.
 
Additional appropriate medical therapy may include but is not limited to: IV fluids, Antihistamines, NSAIDs, Acetaminophen, Narcotics
 
Increase monitoring of vital signs as medically indicated until the participant is deemed medically stable in the opinion of the investigator.
 
If symptoms resolve within 1 hour of stopping drug infusion, the infusion may be restarted at 50% of the original infusion rate (e.g. from 100 mL/hr to 50 mL/hr).
 
Otherwise dosing will be held until symptoms resolve and the participant should be premedicated for the next scheduled dose.
 
Participants who develop Grade 2 toxicity despite adequate premedication should be permanently discontinued from further study drug treatment
	
Participant may be premedicated 1.5h (± 30 minutes) prior to infusion of _____ with: Diphenhydramine 50 mg po (or equivalent dose of antihistamine). Acetaminophen 500-1000 mg po (or equivalent dose of analgesic).

Grades 3 or 4 Grade 3: Prolonged (i.e., not rapidly responsive to symptomatic medication and/or brief interruption of infusion); recurrence of symptoms following initial improvement; hospitalization indicated for other clinical sequelae (e.g., renal impairment, pulmonary infiltrates) Grade 4: Life-threatening; pressor or ventilatory support indicated	
Stop Infusion.
 
Additional appropriate medical therapy may include but is not limited to: Epinephrine**, IV fluids, Antihistamines, NSAIDs, Acetaminophen, Narcotics, Oxygen, Pressors, Corticosteroids
 
Increase monitoring of vital signs as medically indicated until the participant is deemed medically stable in the opinion of the investigator.
 
Hospitalization may be indicated.
 
**In cases of anaphylaxis, epinephrine should be used immediately.
 
Participant is permanently discontinued from further study drug treatment.
	No subsequent dosing

Appropriate resuscitation equipment should be available at the bedside and a physician readily available during the period of drug administration.
 
For further information, please refer to the Common Terminology Criteria for Adverse Events v5.0 (CTCAE) at http://ctep.cancer.gov
		

#### **7.2.1.1.4 Other Allowed Dose Interruption for Pembrolizumab**

Pembrolizumab monotherapy or in combination may be interrupted for situations other than treatment-related AEs such as medical / surgical events or logistical reasons not related to study therapy. Participants should be placed back on study therapy within 3 weeks of the scheduled interruption, unless otherwise discussed with the Sponsor-Investigator. The reason for interruption should be documented in the subject's study record.

#### **7.2.2 Radiation Therapy**

Radiation will be given according to institutional standard/standard of care, and is expected to be administered over an average of 5-6 weeks duration. Radiation therapy may be completed at a local institution, however if radiation therapy is to be planned and administered outside of the research site, the outside Radiation Oncologist will be required to consult with a Consortium-affiliated Radiation Oncologist working on this trial prior to determining eligibility and prior to initiating protocol therapy. Please refer to Table 2 - [Trial Treatment](#) for additional information.

#### **7.2.3 Surgery**

Surgical resection is to be completed per institutional standard/standard of care, after completion of protocol pembrolizumab and radiation therapy. Surgery should be completed no less than 4 weeks from last dose of radiation or last dose of pembrolizumab therapy, whichever is later, and must occur after completion of the End of Treatment visit. Surgery must occur no later than 8 weeks after the last dose of radiation or pembrolizumab therapy, whichever is later. Approval of delays greater than 8 weeks between last dose of study therapy and surgical date may be approved by the Sponsor-Investigator on a case-by-case basis. Subjects who do not proceed to surgery for any reason will be replaced.

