## 4.0 OBJECTIVE(S) & HYPOTHESIS(ES)

### 4.1 Primary Objective(s)

1. To determine the rate of complete histopathologic necrosis following the combination of pembrolizumab and neoadjuvant radiation.

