## 7.4 Subject Withdrawal/Discontinuation Criteria

Subjects may withdraw consent at any time for any reason or be removed from the trial at the discretion of the Sponsor-Investigator for any reason. In addition, a subject may be withdrawn by the Sub-Investigator or the Sponsor-Investigator if enrollment into the trial is inappropriate, the trial plan is violated, or for administrative and/or other safety reasons. When a subject discontinues/withdraws prior to 90 Day Follow-Up Visit, all applicable activities scheduled for the 90 Day Follow-Up visit should be performed at the time of discontinuation.

A subject will be considered withdrawn and no longer followed if they enroll onto hospice care.

A subject must be discontinued from the trial for any of the following reasons:

- The subject or legal representative (such as a parent or legal guardian) withdraws consent.
- Unacceptable adverse experiences as described in Section 7.2.1.1
- Intercurrent illness that prevents further administration of treatment
- Sponsor-Investigator's decision to withdraw the subject
- The subject has a confirmed positive serum pregnancy test
- Noncompliance with trial treatment or procedure requirements
- The subject is lost to follow-up
- Administrative reasons
- Subject progresses (clinically and/or radiologically) and is no longer a surgical candidate.

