## 7.5 Subject Replacement Strategy

Should any subjects fail to complete at least 2 doses of pembrolizumab and surgery, they will be replaced.

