After the Wound Care Follow-Up Visit (or 90 Day Follow-Up Visit if the Wound Care Follow-Up visit is omitted), subjects will be contacted by telephone or medical record review every 12 weeks ( $\pm$  2 weeks) to assess for disease status, recurrence, and survival status until 1 year after initiation of pembrolizumab, death, withdrawal of consent, or the end of the study, whichever occurs first. After the first year, then subjects will be contacted via telephone or medical record review every 6 months ( $\pm$  2 months) to assess for disease status, recurrence, and survival status until 5 years after initiation of pembrolizumab, until death, withdrawal of consent, or the end of the study, whichever comes first.

Female subjects of child-bearing potential must have a negative serum pregnancy test at screening. Subsequent cycles may be either serum or urine tests. If more than 72 hours elapses between screening negative serum pregnancy assessment and C1D1, the negative serum pregnancy should be reconfirmed prior to administration of C1D1 treatment.

End of Treatment disease assessment via imaging must be completed within 3 weeks prior to planned surgery.

Archival tissue may be used instead of fresh biopsy collection. If archival tissue is utilized at baseline, tissue must have been collected within 90 days prior to planned Week 1 Day 1. End of treatment tissue will be collected from surgical resection. If no surgical resection occurs, this tissue will not be collected.

ECOG performance status must be confirmed within 7 days prior to the date of C1D1. If more than 7 days elapse between ECOG assessment and C1D1, the ECOG performance status should be reconfirmed prior to administration of C1D1 treatment.

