## 10.0 STATISTICAL ANALYSIS PLAN

### 10.1 Statistical Analysis Plan Summary

The rationale for combining radiation and immunotherapy has been written about extensively . However, these studies have focused on hypofractionated radiation in the metastatic setting and none of these published studies have examined the use of Pembrolizumab with the neoadjuvant radiation schedules that are typically used in the curative setting for many malignancies. Safety will be evaluated by CTCAE 5.0 and tabulated for qualitative description.

With regards to efficacy analysis, RECIST evaluations will be performed and tabulated in both qualitative and quantitative formats. This is a pilot trial that is not powered to give definitive determination of efficacy. As RECIST partial responses are not typically seen following neoadjuvant radiation alone, any objective responses would be highly interesting and encouraging of further study either for soft-tissue sarcomas generally or for a specific subtype where a response was observed.

The rate of complete necrosis will also be analyzed. It is assumed that the rate of complete necrosis in this subject population is approximately 15% after chemoradiation . A design with 26 subjects has 94.4% power to detect an improvement in the complete necrosis rate from 15% to 40%. The observation of at least 7 subjects with complete necrosis would be considered evidence to rule out a 15% complete necrosis rate. With 26 subjects, binary proportions can be estimated to within 20%. Any toxicity with at least 10% prevalence has at least a 94% chance of being observed.

Event free survival and overall survival at 1 and 5 years will be determined in order to estimate the potential benefit in the highest risk subjects. We will generate Kaplan Meier curves to illustrate these overall survival rates and event-free survival rates. Using data already being analyzed under IRB approved protocols, we will compare these to historical controls at our institution using Cox's proportional hazard model. Subjects' demographic variables (such as age and gender) will be incorporated in the analysis.

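### Replacement can follow from a treatment outcome, and section 10.1 gives replaced subjects no place in the primary necrosis rate, so 7 of 26 most naturally describes completers only

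*Combined protocol and SAP*

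**What the plan says.** The primary objective (section 4.1) is "To determine the rate of complete histopathologic necrosis following the combination of pembrolizumab and neoadjuvant radiation".

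Two rules govern replacement. Section 7.2.3: "Subjects who do not proceed to surgery for any reason will be replaced". Section 7.5: "Should any subjects fail to complete at least 2 doses of pembrolizumab and surgery, they will be replaced".

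Section 7.4 lists the reasons for mandatory discontinuation. Two of them are outcomes of treatment: "Subject progresses (clinically and/or radiologically) and is no longer a surgical candidate" and "Unacceptable adverse experiences as described in Section 7.2.1.1".

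On post-treatment tissue, a footnote to the schedule in section 8.1 states: "If no surgical resection occurs, this tissue will not be collected".

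Section 10.1 sets the benchmark, "It is assumed that the rate of complete necrosis in this subject population is approximately 15% after chemoradiation", and the decision rule, "The observation of at least 7 subjects with complete necrosis would be considered evidence to rule out a 15% complete necrosis rate". It gives 26 subjects and 94.4% power for 15% against 40%. It names no analysis set for necrosis and does not say how replaced subjects, or subjects without a specimen, are counted. The trial summary gives 26 subjects without saying whether replaced subjects are among them. Only the adverse event endpoint (section 5.2) is stated to cover all subjects.

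**The concern.** A subject whose tumour progresses beyond resection on treatment, or who stops for toxicity before the second dose, is replaced. If the replaced subject is left out of the analysis, a failure of the regimen leaves the denominator of the rate meant to describe the regimen.

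A reader of the result could not tell whether the rate is per treated or per completing subject. Section 6.2.3.1 says a significant improvement in this rate would be a strong reason to pursue a randomized trial, so the denominator bears on that decision. The trial is open-label, and a denominator not fixed in advance can be chosen after the results are seen.

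Toxicity information is not lost, because adverse events are reported for all subjects.

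**Working it through.** **Inputs from the documents.** N = 26, cut-off 7, null rate 15%, alternative 40% and stated power 94.4%, all from section 10.1. No alpha and no expected replacement rate are stated.

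**The plan's own figure.** With X ~ Binomial(26, p):
- P(X ≥ 7 | p = 0.40) = 0.9441, which reproduces the stated 94.4%.
- P(X ≥ 7 | p = 0.15) = 0.0833, so the implied one-sided error is 8.3%.
- Neighbouring cut-offs do not match: 6 gives power 0.979 and error 0.185; 8 gives power 0.878 and error 0.032.

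The calculation needs a necrosis result in all 26 subjects. Replacing unresected subjects is how 26 results are obtained, which is why the completer reading is the natural one. It remains an inference from the plan's silence.

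**Direction.** Subjects replaced without resection have no post-treatment tissue. If non-resection counts as not complete necrosis, adding them enlarges the denominator only, so the completer rate can only equal or exceed the all-treated rate. Subjects resected after one dose are also replaced under section 7.5, but they have a pathology result and can move the rate either way:
- 6/26 = 23.1% plus two with complete necrosis gives 8/28 = 28.6%.
- 7/26 = 26.9% plus two without gives 7/28 = 25.0%.

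**Effect on the decision rule.** Let d be the fraction of treated subjects who are replaced (assumed: 5% to 20%). Suppose the true all-treated rate is 15% and no replaced subject is credited with complete necrosis. Then the completer rate is 0.15/(1 − d), and the expected number replaced to obtain 26 completers is 26d/(1 − d).

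| d | Expected replaced | Completer rate | P(X ≥ 7 of 26) |
|---|---|---|---|
| 0% | 0 | 15.0% | 8.3% |
| 5% | 1.4 | 15.8% | 10.4% |
| 10% | 2.9 | 16.7% | 12.9% |
| 15% | 4.6 | 17.6% | 16.1% |
| 20% | 6.5 | 18.8% | 20.2% |

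If 15% is instead the rate among completers, the last column is 8.3% in every row.

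A milder case: suppose half the replaced subjects would have had the completer rate and the other half no complete necrosis. The completer rate is then 0.15/(1 − d/2), and P(X ≥ 7 of 26) is 9.3%, 10.4%, 11.6% and 12.9% for d = 5%, 10%, 15% and 20%.

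**Effect on the estimate.** Seven complete necroses among 26 completers, with m unresected replaced subjects added to the denominator (Clopper-Pearson intervals):

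| m | Rate | Exact 95% CI |
|---|---|---|
| 0 | 7/26 = 26.9% | 11.6–47.8 |
| 1 | 7/27 = 25.9% | 11.1–46.3 |
| 3 | 7/29 = 24.1% | 10.3–43.5 |
| 5 | 7/31 = 22.6% | 9.6–41.1 |
| 7 | 7/33 = 21.2% | 9.0–38.9 |

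**The case against.** Necrosis can be read only on a resection specimen, and replacing subjects who cannot be evaluated is a recognised choice in a pilot. The plan discloses it in two places. Section 10.1 also says the trial is not powered for a definitive efficacy conclusion.

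The inflated error arises only if the 15% is an all-treated rate. A rate per resected patient is at least as plausible, and against it the completer rate is the like-for-like comparison. The 10.4% to 20.2% series is also a worst case. Replacement for any reason covers withdrawal of consent, pregnancy, loss to follow-up and administrative reasons, and a subject stopped for toxicity after two doses who is then resected is not replaced. Nothing in the documents points to 15% or 20% replaced, and entry requires planned surgery with curative intent. With one to three replacements the estimate falls only to between 25.9% and 24.1%, small beside the plan's stated precision of 20 percentage points. Finally, a fix that keeps the cut-off at 7 leaves the chance of reaching it unchanged.

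Most of this stands as a limit on size. The error figures are conditional and at the upper end, and the effect is modest if replacements are few. It does not supply a denominator: the plan sets a numerical rule to rule out 15%, and that rule needs a stated population. Scoring non-resection as failure is one convention among several, so the all-treated rate should be shown beside the completer rate, not in place of it. Keeping the cut-off is coherent once the rule is labelled as applying to completers.

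**Conclusion.** The concern holds and should be fixed. The replacement rules can remove on-treatment failures, and section 10.1 does not say how replaced subjects count in the primary rate. This much is read directly from the text. That 7 of 26 describes completers is the natural reading, not a stated one.

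The 94.4% power is arithmetically correct. On the completer reading, it and the implied 8.3% error apply to the rate among completers and not to the all-treated rate. How far the result misleads depends on two things the documents do not give: the replacement rate, and whether the 15% benchmark is per treated or per resected patient. If it is per treated patient and no replaced subject is credited, the error is 10.4% to 20.2% for 5% to 20% replaced. If it is per resected patient, there may be little or no bias against 15%, but the reported rate would still not describe everyone who started the combination.

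**What to change.** In section 10.1:

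1. Define an all-treated set (at least one dose of pembrolizumab). Count subjects without resection as not having complete necrosis, and count subjects resected after one dose by their pathology.
2. Report the complete necrosis rate with an exact confidence interval in this set beside the rate among the 26 completers, with the number of and reasons for replacements.
3. State that the 7-of-26 rule, with its 8.3% error and 94.4% power, applies to completers only.
4. State whether the 15% benchmark is per treated or per resected patient, so that the like-for-like comparison is identified.

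The cost is text in one section. No assessments are added, and the replacement rules, sample size, cut-off and power among completers do not change. The drawback is that two rates must be presented and the all-treated one may be lower. If completers have a 40% rate and no replaced subject is credited, the all-treated rate is 0.40 × (1 − d), that is 38%, 36%, 34% or 32% at 5%, 10%, 15% or 20% replaced.
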